#### **2.5.4 Supportive analyses**

The raw value, ratio to baseline and log-transformed ratio to baseline of UACR will be plotted for each subject over time.

Absolute change from baseline in UACR and 24 hour UALB will also be analyzed using MMRM and ANCOVA, respectively.

The following supplementary analyses for UACR will be performed CCI separately.

1. Use value from Day 1 24 hour urine collection instead of last measurement prior to 1st dose as the baseline. Subjects without Day 1 value will be excluded from analysis.
2. Set assessments to missing if they were taken after dose reduction/interruption due to AEs and physician decision
3. Exclude subjects with baseline UACR < 300
4. Include all data from all randomized subjects and use the assigned treatment instead of the actual treatment received in the analysis (Intention to Treat, i.e., ITT)
5. Exclude week 24 measurements taken on day 134 or earlier from the ITT analysis
6. Exclude subjects with baseline UACR > 14000

The following supplementary analyses for 24 hour UALB will be performed separately.

1. Set assessments to missing if they were taken after dose reduction/interruption due to AEs and physician decision
2. Exclude subjects with baseline UACR < 300
3. ITT analysis
4. Exclude week 24 measurements taken on day 134 or earlier from the ITT analysis

## **2.6 Analysis of secondary efficacy objective(s)**

### **2.6.1 Efficacy and/or Pharmacodynamic endpoint(s)**

Log-transformed ratio to baseline for eGFR, free water clearance, HbA1c and fasting lipid profiles (total cholesterol, HDL, LDL, triglycerides and Lp(a)) as well as % change from baseline in weight and change from baseline in BMI and WTH ratio will be analyzed using the same MMRM described in [Section 2.5.2.2](#) with baseline in lieu of log-transformed baseline as a covariate for change from baseline analysis. For parameters with only one post-treatment measurement, an ANCOVA with treatment as a classification factor and baseline (or log-transformed baseline if applicable) as a covariate will be employed.

The raw value, change from baseline, ratio to baseline and log-transformed ratio to baseline of HbA1c will be plotted for each subject over time.

The free water clearance (mL/min) will be calculated using the following formula:

$$\frac{(\text{Total Volume (mL)} / \text{Elapsed Date \& Time (min)}) * (1\text{-}24 \text{ hr Urine Osmolality (mOsmol/kg)} / \text{Serum Osmolality (mOsmol/kg)})$$

The result of free water clearance will be rounded to one decimal place prior to statistical analysis.

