### **8.3.1 Renal function assessments, markers of diabetic nephropathy**

The following assessment will profile renal function, which are markers of diabetic nephropathy:

- Urine albumin-creatinine ratio (UACR) at serial time points, as specified in the [Assessment Schedule](#)

- 24-hour urinary collection at baseline and end of study, measured for albumin
- Estimated glomerular filtration rate (eGFR), as determined by the Chronic Kidney Disease Epidemiology Collaboration (CKD-EPI) equation. ([Levey and Stevens 2010](#))
- Free water clearance

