## 1.2 Study objectives and endpoints

Objective(s)	Endpoint(s)
Primary objective(s)	Endpoint(s) for primary objective(s)

 
To compare the effect of nidufexor to placebo on albuminuria in patients with diabetic nephropathy already receiving treatment with ACEI or ARB
 
	
 
Urine albumin-creatinine ratio (UACR) at serial time points, as specified in the assessment schedule in the protocol
 
24-hour urinary albumin at baseline and end of study
 

 
To assess the safety and tolerability of nidufexor
 
	
 
Safety endpoints including: 
 
vital signs
 
physical examination
 
laboratory measurements
 
ECG parameters
 
adverse events
 
 
 

Secondary objective(s)	Endpoint(s) for secondary objective(s)

 
To determine the effect of nidufexor on renal filtration function
 
	
 
Estimated glomerular filtration rate (eGFR), as determined by the Chronic Kidney Disease Epidemiology Collaboration (CKD-EPI) equation (Levey and Stevens 2010)
 

 
To assess the pharmacokinetic properties of nidufexor on day 1 and at steady state in patients with type 2 diabetes and nephropathy
 
	
 
Cmax, Tmax and AUC0-6h.
 

 
To determine the effect of nidufexor on renal tubular function
 
	
 
Free water clearance
 

 
To determine the effect of nidufexor on anthropometric assessments
 
	
 
Assessments 
 
Weight
 
BMI
 
Waist-to-hip (WTH) ratio
 
 
 

 
To determine the effect of nidufexor on lipids
 
	
 
Fasting lipid profile, including lipoprotein (a) [Lp(a)]
 

---

Objective(s)	Endpoint(s)
---------------------	--------------------

---

Commercially Confidential Information

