### **2.5.2.2 Efficacy and/or pharmacodynamic endpoints**

For all efficacy PD analyses, the PD set will be used.

A Mixed Model for Repeated Measures (MMRM) analysis will be performed for log-transformed ratio to baseline UACR measured at each visit. The model will include effects for log-transformed baseline, treatment, visit, treatment by visit interaction and visit by log-transformed baseline interaction. An unstructured variance-covariance matrix will be used to account for correlation among multiple measurements from the same patient and variance heterogeneity.

Similarly an Analysis of Covariance (ANCOVA) with treatment as the classification factor and log-transformed baseline as the covariate will be conducted for log-transformed ratio to baseline 24-hour urine albumin excretion.

Point estimates, the associated confidence intervals as well as the p-values for treatment difference at each visit will be provided within the MMRM/ANCOVA framework. The null hypothesis of no treatment difference in UACR or 24-hour urine albumin excretion will be tested at the one-sided 0.1 significance level. A treatment difference of at least 25% in favor of LMB763 will be considered clinically significant.

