### **2.5.3 Handling of missing values/multiple values/censoring/discontinuations.**

Missing data will not be imputed.

Assuming data is missing at random, a patient with a missing value at a visit will still contribute to the estimation of the treatment effect at that particular visit as the likelihood-based MMRM borrows information from non-missing values of this patient and other patients.

For central lab data collected at scheduled visits, the following sequential approach will be taken before data summary and analysis.

1. Take the average by subject, date and time for each parameter first.
- 2a. Derive baseline as the last available value prior to Day 1 dosing for each subject and parameter.
- 2b. Take the average by subject and visit for each parameter and then merge with the dataset containing baseline from 2a by subject and parameter.

The same approach as described above will be taken for vital sign and VAS data.

Local lab data will be included along with central lab data in the data listings and liver/renal event tables.

For ECG, 3 measurements on each visit are expected. The mean value will be used in the analyses even though the times are different.

For the analyses of liver abnormality and renal events, the most extreme value expressed as the multiple of the upper limit of normal (xULN) in a visit will be used for analyses.

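### Free water clearance can be zero or negative, so its planned log ratio to baseline is undefined for some patients and can reverse direction for others

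*SAP*

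**What the plan says.** SAP 2.6.1 places free water clearance in the group analysed on the log scale: "Log-transformed ratio to baseline for eGFR, free water clearance, HbA1c and fasting lipid profiles". Protocol 12.5.1 does the same. BMI and waist-to-hip ratio are instead analysed as change from baseline with untransformed baseline as covariate.

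SAP 2.6.1 then gives the formula: total volume divided by elapsed minutes, times one minus 24-hour urine osmolality over serum osmolality. It adds: "The result of free water clearance will be rounded to one decimal place prior to statistical analysis".

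Two models could apply:

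- The repeated-measures model of SAP 2.5.2.2: "The model will include effects for log-transformed baseline, treatment, visit, treatment by visit interaction and visit by log-transformed baseline interaction".
- For parameters measured once after treatment starts, an ANCOVA in which "baseline (or log-transformed baseline if applicable) as a covariate will be employed".

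Protocol 8.3.1 describes a "24-hour urinary collection at baseline and end of study, measured for albumin", and the 24-hour collection footnote to Protocol Table 8-1 adds volume and osmolality. The ANCOVA therefore probably governs.

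On missing values, SAP 2.5.3 states: "Missing data will not be imputed". Neither document shows an offset, an exclusion rule or another scale for zero or negative values.

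**The concern.** A log ratio to baseline suits quantities that are always positive, such as UACR, eGFR or lipids. Free water clearance is signed, and its sign carries the physiological meaning: positive when urine is more dilute than serum, negative when it is more concentrated. The formula and the analysis scale in SAP 2.6.1 are therefore incompatible for any patient whose urine is as concentrated as serum, or more so, at either visit.

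Free water clearance is the only endpoint listed in SAP 1.2 for the objective "To determine the effect of nidufexor on renal tubular function". Patients could drop out of its analysis because of the value measured at Week 24, that is, after randomisation and possibly because of treatment. The missing-at-random argument in SAP 2.5.3 does not cover this, because such a value is lost because of its own sign. Alternatively, patients could stay in with the direction of their change reversed. Any repair chosen after seeing the data would be data-driven.

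**Working it through.** The documents state no power or precision for this endpoint, so there is no plan figure to reproduce. The check is algebra from the SAP formula, followed by an illustration under stated assumptions.

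**1. Sign of the quantity.** Write FWC = (V/t) × (1 − U/S), with V urine volume, t minutes, U urine osmolality and S serum osmolality. Take V = 2000 mL, t = 1440 min and S = 290 mOsmol/kg (assumed). Then V/t = 1.389 mL/min.

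| U (mOsmol/kg) | FWC (mL/min) | Rounded |
|---|---|---|
| 200 | 1.389 × (1 − 200/290) = 0.431 | 0.4 |
| 290 | 0 | 0.0 |
| 400 | −0.527 | −0.5 |
| 500 | −1.006 | −1.0 |

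**2. Effect of rounding.** Any absolute value below 0.05 becomes 0.0, so zero is a band and not a point. Its half-width in U is 0.05 × 290 × 1440/V. The band is about 269 to 311 mOsmol/kg at 1 L/day, 280 to 300 at 2 L/day and 283 to 297 at 3 L/day.

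**3. Log ratio, case by case.**

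| Baseline to Week 24 | Change | Ratio | Log ratio |
|---|---|---|---|
| +0.5 to +1.0 | +0.5 | 2.0 | +0.693 |
| −0.5 to −1.0 | −0.5 | 2.0 | +0.693 (reversed) |
| −1.0 to −0.5 | +0.5 | 0.5 | −0.693 (reversed) |
| −0.5 to +0.3 | +0.8 | −0.6 | undefined |
| +0.3 to −0.5 | −0.8 | −1.67 | undefined |
| 0.0 to −0.5 | −0.5 | none | undefined |

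The log of baseline is also undefined for every baseline at or below zero.

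**4. The two covariate readings.** With log-transformed baseline, only patients positive at both visits can enter the model. With untransformed baseline, patients negative at both visits enter with their direction reversed, while zeros and sign changes still fail because the outcome is a log ratio.

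**5. How many patients.** The simulation assumes S = 295 mOsmol/kg, V with mean 2000 and SD 500 mL/24 h (floor 500, independent between visits), U normal (floor 50) with within-patient correlation 0.6, and rounding to 0.1.

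| Mean (SD) of U | Negative at one visit, unrounded | Both positive | Both negative | Log ratio undefined |
|---|---|---|---|---|
| 200 (80) | 12% | 77% | 3.5% | 20% |
| 300 (80) | 52% | 27% | 32% | 41% |
| 500 (150) | 91% | 3% | 84% | 13% |

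With correlation 0.3 or 0.8, the both-positive share is 74% or 79% at mean 200, and 1% or 4% at mean 500.

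**6. What an effect would look like.** Suppose also that U on active is 50 mOsmol/kg lower at Week 24. For mean U of 200, 300 and 500:

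- ANCOVA on absolute change gives a nearly constant +0.22 to +0.24 mL/min.
- Log ratio with log-transformed baseline gives ratios of about 1.4, 1.4 and 1.2. These come from 77%, 27% and 3% of placebo patients against 83%, 36% and 4% of active patients.
- Log ratio with untransformed baseline gives about 1.4, 1.1 and 0.8, so one and the same effect reads as an increase, almost nothing, or a decrease.

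**The case against.** The algebra is hard to dispute; the case on the other side concerns emphasis.

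- **Reversal depends on the covariate.** The more natural reading of SAP 2.6.1 uses log-transformed baseline for log-ratio endpoints. A patient negative at both visits then drops out, and no reversed value enters the model. This stands: under that reading the defect is selective loss of patients, and reversal would appear only in summaries of the log ratio. The wording *if applicable* does leave the other reading open.
- **The percentages are not from the trial.** This also stands. Neither document gives osmolality, volume, correlation or an expected shift, and the results span nearly the whole scale. They show that the problem can range from moderate to near total. Even the most dilute scenario leaves about a fifth of pairs undefined.
- **Formula and visit timing are partly inferred.** The formula is damaged in the text available, and the urine rows of Protocol Table 8-1 are not visible. Reading it as one minus the osmolality ratio is the only version that matches the endpoint's name. The defect does not depend on the number of visits.
- **Consequence is limited.** This is one secondary endpoint in a non-confirmatory trial, and a programmer would notice undefined logs. That is true, but noticing them at analysis is when an unplanned choice would be made.

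**Conclusion.** The concern holds. As written, the analysis of free water clearance cannot be run validly on all patients: the log ratio fails for zeros and sign changes, and a log baseline fails for every non-positive baseline. If untransformed baseline is used, patients negative at both visits contribute in the wrong direction. This follows from the SAP's own formula and needs no clinical assumption.

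How many patients are affected cannot be determined from the documents. Under the assumptions shown, between 3% and 77% would be usable with log-transformed baseline. The only endpoint for renal tubular function is compromised. The primary UACR and 24-hour albumin analyses and the UACR-based Go/No-Go rule are untouched. It should be corrected before analysis.

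**What to change.** In SAP 2.6.1, move free water clearance from the log-ratio group to the change-from-baseline group: absolute change in mL/min, with untransformed baseline as covariate. Every case in the table of step 3 is then defined and keeps its direction. The planned rounding can stay; under the same assumptions it adds 0.1% to 0.6% to the SD of the change.

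Make the matching edit in Protocol 12.5.1. Protocol 14.1 requires a written, approved amendment for that, so the quicker route is to change the SAP alone and record the departure in SAP Section 3, which at present declares none. The cost is one sentence in the SAP, the entry in SAP Section 3 if the protocol is left as it is, and one sentence in the protocol when it is next amended. No new data are needed.

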## 2.7 Pharmacokinetic endpoints

LMB763 plasma concentration data will be listed by patient and visit/sampling time point. Descriptive summary statistics will be provided by visit/sampling time point,

Commercially Confidential Information

Summary statistics will include mean (arithmetic and geometric), SD, CV (arithmetic and geometric), median, minimum and maximum. An exception to this is Tmax where median, minimum and maximum will be presented.

Commercially Confidential Information

The following pharmacokinetic parameters will be determined using the actual recorded sampling times and non-compartmental method(s) with Phoenix WinNonlin (Version 6.2 or higher): Cmax, Tmax, and AUClast from the plasma concentration-time data. The linear trapezoidal rule will be used for AUC calculation.

## 2.8 PD and PK/PD analyses

The relationship between key efficacy/PD parameters (including, but not limited to UACR, 24-hour urine albumin excretion and eGFR) and LMB763 PK parameters (Cmax and AUC0-6) may be explored using a graphical approach. Additional statistical analysis such as regression may be performed, if necessary. Modeling approach may also be used to explore the PK/PD interactions as well as effect of covariates and their significance on the PK/PD relationship.

## 2.9 Patient-reported outcomes

Change from baseline itch VAS measurements will be analyzed using the same MMRM described in [Section 2.5.2.2](#).

Commercially Confidential Information

Commercially Confidential Information

Commercially Confidential Information

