### **8.5 Additional assessments**

#### **8.5.1 Clinical Outcome Assessment - Visual Analog Scale (VAS)**

The participant must be given the PRO measure(s) to be completed at the scheduled visit before any clinical assessments are conducted. Participant's refusal to complete all or any part of a PRO measure should be documented in the study data capture system and should not be captured as a protocol deviation. Handling of protocol deviations can be modified if needed.

Participant questionnaires should be completed in the language most familiar to the participant.

The participant should be given sufficient space and time to complete the PRO measure(s).

The site personnel or delegate should check PRO measure(s) for completeness and ask the participant to complete any missing responses. The responses stored electronically in the database will be considered the source file.

Completed measure(s) (including when using paper PRO measures and any unsolicited comments written by the participant) must be reviewed and assessed by the investigator for responses which may indicate potential AEs or SAEs before any clinical study examinations are performed. This assessment should be documented in study source records. If AE or SAE are confirmed, the study investigator should not encourage the participant to change responses reported in the completed questionnaires. Study investigators must follow reporting instructions outlined in [Section 10.1.1](#) of the study protocol.

A 10 cm visual analogue scale (VAS) will be used to assess the severity of patients itch (ranging from 0 = no itch at all, to 10 = the worst itch imaginable itch). The score (distance from left) on the VAS will be recorded by the patient by marking with a line and used to test for an effect of nifedexor over placebo. The scale will be completed by patients as indicated in [Table 8-1](#) (Assessment schedule).

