### **12.4.2.2 Efficacy and/or Pharmacodynamic Endpoints**

For all efficacy PD analyses, the PD set will be used.

A repeated measures Analysis of Covariance (ANCOVA) will be performed for log-transformed ratio to baseline UACR measured at each visit. The model will include effects for log-transformed baseline, treatment, visit, treatment by visit interaction and visit by log-transformed baseline interaction. An unstructured variance-covariance matrix will be used to account for correlation among multiple measurements from the same patient and variance heterogeneity.

Similarly an ANCOVA with treatment as the classification factor and log-transformed baseline as the covariate will be conducted for log-transformed ratio to baseline 24-hour urine albumin excretion.

Point estimates, the associated confidence intervals as well as the p-values for treatment difference at each visit will be provided within the ANCOVA framework. The null hypothesis of no treatment difference in UACR or 24-hour urine albumin excretion will be tested at the one-sided 0.1 significance level. A treatment difference of at least 25% in favor of nidufexor will be considered clinically significant.

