#### **12.5.6 Patient reported outcomes**

Change from baseline itch VAS measurements will be analyzed using the same repeated measures ANCOVA described in [Section 12.4.2](#).

Commercially Confidential Information

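### The itch VAS is assigned the UACR model with log-transformed baseline as covariate; taken literally, that covariate is undefined for every patient whose baseline itch score is 0

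*SAP*

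**What the plan says.** SAP 2.9 assigns the itch VAS to a model by cross-reference: "Change from baseline itch VAS measurements will be analyzed using the same MMRM" as in SAP 2.5.2.2. It states no modification. Protocol 12.5.6 does the same with reference to Protocol 12.4.2: "Change from baseline itch VAS measurements will be analyzed using the same repeated measures ANCOVA described in" that section.

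The model referred to was written for the log-transformed ratio to baseline of UACR. SAP 2.5.2.2 specifies it as follows: "The model will include effects for log-transformed baseline, treatment, visit, treatment by visit interaction and visit by log-transformed baseline interaction". Protocol 12.4.2.2 has the same terms, including the "visit by log-transformed baseline interaction".

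Protocol 8.5.1 describes the VAS as a 10 cm line that the patient marks, "ranging from 0 = no itch at all" up to 10 for the worst itch. It says that the score will be used to test for an effect of the drug over placebo.

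An exception to the log covariate does exist. SAP 2.6.1 runs the same model "with baseline in lieu of log-transformed baseline as a covariate for change from baseline analysis", and Protocol 12.5.1 says the same. In both places the sentence covers a named list: eGFR, free water clearance, HbA1c, lipids, weight, BMI and waist-to-hip ratio. The VAS is not on it.

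SAP 2.5.3 applies averaging and a baseline derivation to VAS data and mentions no offset. It also says that missing values are not filled in.

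**The concern.** A score of 0 is a legitimate baseline value on this scale, and the logarithm of 0 is undefined. A likelihood-based repeated-measures model can use a patient with a missing outcome at some visits, but not a patient with no covariate value. All visits of that patient are lost.

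The loss would be selective. Patients who start at 0 are those in whom new itch appears against a clean background, so the fitted treatment difference would describe only patients with a non-zero score before dosing. Protocol 1.1.6 reports itch as the most common adverse event in the earlier NASH study, and the Protocol summary lists the itch VAS among the key safety assessments. SAP 2.5.2.1 rules out formal analysis of safety and tolerability data, so in the visible text the VAS model is the only planned model-based comparison of itch between arms.

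**Working it through.** **The plan's own figure.** The documents give no power or precision for the VAS. The one stated power figure, in Protocol 12.8.1, concerns UACR: 72% for the dual criterion with 50 patients per arm, SD 0.6, a true reduction of 30%, an estimated reduction of at least 25%, and one-sided 0.10.

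- SE = 0.6 × √(2/50) = 0.12.
- Clinical threshold: −ln 0.75 = 0.288. Statistical threshold: 1.282 × 0.12 = 0.154. The clinical one binds.
- True effect: −ln 0.70 = 0.357.
- Power = 1 − Φ((0.288 − 0.357)/0.12) = 0.717. A simulation of 200,000 trials with the t-test also gives 0.717.

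The figure reproduces, and nothing in this point touches it.

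**The VAS specification, step by step.**

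1. Outcome: change from baseline in VAS (SAP 2.9).
2. Covariates: log-transformed baseline and its interaction with visit (SAP 2.5.2.2, by cross-reference).
3. Admissible baseline values: 0 to 10 (Protocol 8.5.1).
4. Baseline: the last value before first dose (SAP 2.1 and 2.5.3). No constant is added before taking logs.
5. For baseline = 0, ln(0) is undefined, so both covariate terms are missing at every visit.
6. Nothing is imputed (SAP 2.5.3), so the patient contributes no record.

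**Size of the loss.** Let p be the share of patients with baseline VAS exactly 0. The documents do not give p, so the values below are assumptions. Patients lost = 116p, and patients kept = 116(1 − p). If zeros are spread evenly over the arms and the residual SD is unchanged, the SE of the treatment difference rises by 1/√(1 − p).

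| p (assumed) | Lost of 116 | Kept of 116 | SE factor |
|---|---|---|---|
| 10% | about 12 | about 104 | 1.05 |
| 25% | 29 | 87 | 1.15 |
| 50% | 58 | 58 | 1.41 |
| 75% | 87 | 29 | 2.00 |

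**Illustration.** A data set of 100 patients with seven records each was simulated, and 48 had a zero baseline. A random-intercept model was fitted as a simplification of the unstructured model. With log baseline it kept 100 − 48 = 52 patients (52 × 7 = 364 records). With untransformed baseline it kept all 100 (700 records).

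**The case against.** The strongest reply is that the intended covariate is easy to infer. The UACR model cannot be carried over unchanged anyway, because its outcome is a log ratio and the VAS outcome is a change from baseline. SAP 2.6.1 already shows the sponsor's convention for change-from-baseline outcomes, which is untransformed baseline. On this view the omission in SAP 2.9 is a drafting slip that would surface the first time the model was run.

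Much of that stands. A reader might infer that the plan means to exclude patients without baseline itch. The documents do not say so; the loss follows only from applying the text as written. The slip still should not be left to silent repair. Untransformed baseline, an added constant before the log, and dropping patients are different analyses, and the text does not choose among them. Protocol 6.4.2 and Table 6-4 also allow the study statistician access to treatment codes throughout, and the programmers from treatment allocation onward, so the choice is better written down beforehand.

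A reader might also infer that the assessment of itch as a whole depends on this model. It does not. SAP 2.5.2.1 summarises adverse events by preferred term and maximum CTCAE grade, and plots pruritus events by grade and against dosing for each subject. None of this uses the VAS model. The VAS is also absent from the visible lists of primary and secondary endpoints.

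Finally, redacted blocks follow the VAS sentence in both documents. The sentence is complete as it stands, but one cannot exclude that further VAS text exists.

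**Conclusion.** The point holds as an error in the written specification of a non-primary analysis. Followed exactly, SAP 2.9 gives an undefined covariate for each patient with a zero baseline and removes those patients from the only visible model-based comparison of itch. Protocol 12.5.6 has the same wording.

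The textual gap is certain; the size of its effect is not. No specific patient count can be claimed, because the share of exact zeros on a marked line depends on the population and on how the mark is measured, and neither is documented. The tabulated range shows only how the loss scales. The SE factors also assume equal loss in both arms and an unchanged residual SD. A reader might infer a threat to the efficacy conclusion, but the Go criterion in Protocol 12.8.1 uses UACR alone, so neither it nor the UACR analysis is affected. The correction is worth making because the loss is selective and the remedy is small.

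**What to change.** In SAP 2.9, state that the VAS model uses untransformed baseline VAS and its interaction with visit in place of log-transformed baseline, as SAP 2.6.1 does for other change-from-baseline endpoints. With that covariate no patient is lost because of a zero baseline.

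The cost is one sentence in the SAP, with no change to data collection or sample size. A protocol change needs a written amendment and approvals (Protocol 14.1), which this point alone does not justify. Protocol 12.5.6 can be aligned if the protocol is amended for other reasons.
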